Screening visit(s). Screening procedures may be scheduled across more than 1 day to meet participant schedules. Prior to completing any study-related screening, participants will review and sign an informed consent form with a trained staff member. Participants will be given the opportunity to do an in-person or a remote consent. For participants that complete the remote consent, some screening procedures will also be completed remotely, including interviews and questionnaires. Participants who complete this initial eligibility screening will complete the remainder of their screening visit in person. During the screening visit, participants will be assessed for inclusion and exclusion criteria. A urine drug-screen will be collected to assess for recent drug exposure and pregnancy (when indicated), the Mini-International Neuropsychiatric Interview (M.I.N.I.), the Addiction Severity Index (McLellan, Cacciola, & Zanis, 1997), the Columbia Suicide Severity Rating Scale, a demographic questionnaire, and a health form assessing current conditions and medications will be used to help evaluate participant eligibility.

Baseline/Randomization visit. Following determination of eligibility, participants will be randomized (stratified by gender) to receive 20mg of SUVO (the maximum FDA approved dose) or placebo. Randomization will occur prior to visit 1. At the randomization visit, participants will provide a urine sample that will be tested for recent drug use and complete self-report measures as described below. They may also complete a cue-induced craving paradigm, a probabilistic reward task, and the Trier Social Stress Test (TSST) described below. Participants will also be provided with an actigraph-like device to wear for the duration of their study participation to assess sleep.

Medication dispensing will begin during the baseline session. Participants will receive a blister package with 7-days of medication dispensed as two capsules (10mg SUVO or placebo) so that medication doses can be reduced to 50% of the dose if requested by a

Date: 09/19/2024

Principal Investigator: [name].

Application Number: IRB00341328

participant. Participants will also receive a 3-day blister package as a contingency strategy in case of missed visits. Participants will be instructed to return blister packages once weekly as a measure of medication compliance.

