We are proposing to administer SUVO 20mg, which is an FDA-approved dose. We are not requiring insomnia as an inclusion criterion in order to focus more specifically on opioid-stimulant co-use behaviors. We have collected substantial evidence that SUVO is safe and does not increase risk of misuse in persons with OUD (see Huhn et al., 2022).

- c. Justification and safety information if non-FDA approved drugs without an IND will be administered.

SUVO is an FDA-approved medication. We are not submitting for an IND because the intervention is not intended to be reported to the FDA as a well-controlled study or for a significant label change, it is not intended to support a significant change in the advertising for the product, and it does not involve a route or dose level or patient population for which there is increased risk associated with use of the drug.

7. Study Statistics

- a. Primary outcome variable

Urine drug-screen results. Participants will complete a urine drug screen at each clinic visit. The presence or absence of non-prescribed opioids and/or cocaine will be recoded at twice-weekly sessions. The primary outcomes will be 1) the presence of absence of opioids at each screen, 2) the presence or absence of cocaine at each screen, and 3) the presence or absence of a screen that is negative for all illicit substances.

Self-reported opioid and cocaine craving. Participant will complete visual analogue scale measures of opioid and cocaine craving during each weekly visit. The average score across each visual analogue scale will be a primary outcome.

Opioid and cocaine cue reactivity. Participants will also complete visual analogue scales in the presence of drug cues. Average scores on visual analogue scales will serve as a primary outcome

- b. Secondary outcome variables.

Insomnia Severity Index Scores. The Insomnia Severity Index is a seven-item screening measure of insomnia. Items are rated on a five-point scale. A cut score of 15 is typically used to demarcate clinical insomnia. The scale has been shown to have excellent psychometric properties, including among patients with substance use disorders.

Sleep Continuity. Using actigraphy and sleep-diaries (in which persons will be asked to report on their sleep the night before the assessment), we will focus on three commonly used sleep continuity outcomes: 1) total sleep time (TST), or the total number of minutes that an individual

Date: 09/19/2024

Principal Investigator: [name].

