Application Number: IRB00341328

is asleep, 2) wake after sleep onset (WASO), or the total number of minutes that an individual is awake after sleep onset and prior to awakening, and 3) subjective sleep quality.

Co-occurring affective symptoms. Participants will be assessed for positive and negative affect using the PANAS. Participants will report perceived stress using the Perceived Stress Scale (PSS) is a 10-item measure of perceived stress. Items are rated on a five-point scale.

Abuse Liability Assessments (i.e., Medication Satisfaction Questionnaire). Participants will be asked to complete abuse liability measures. Participants will also be assessed for adverse events and serious adverse events in each visits. The abuse liability of the blinded study drug will be assessed by asking participants to rate “drug effects”, “good effects”, and “bad effects”, on a 0-100 point VAS, with 0 being “None” and 100 being “Extremely”. Participants will also report the perceived street value of the study drug. These subjective drug effect ratings are considered by the FDA to be the gold standard for assessing abuse liability.

Adverse events We will follow standard FDA guidelines regarding adverse events. Participants will be able to self-report adverse events via a study contact number. Events will be documented on a standardized form that adheres to FDA standards for adverse event reporting (e.g., event, system affected, start and stop date/time, perceived relationship to the study, severity, expectedness).

c. Statistical plan including sample size justification and interim data analysis.

Primary Aim 1. To examine whether SUVO 20mg reduces opioid and cocaine use and craving relative to placebo, a series of mixed models will be conducted. For analyses with a binary outcome (i.e., use at each assessment), generalized logistic models will be used, and for analyses with a continuous outcome (i.e., craving), linear mixed models will be used. Mixed effects models will also be used to compare drug cue reactivity at baseline and during the final week. For each model, we will include main effects of timepoint and medication group, as well as an interaction term. If the two treatment groups are systematically different on demographic or use characteristics at baseline, these measures will be included as covariates in the analysis. Models will involve a random intercept.

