Secondary Aim 1 and 3. To examine whether SUVO 20 mg improves 1) insomnia symptoms, 2) indices of sleep continuity, and 3) co-occurring affective symptoms relative to placebo, a series of mixed effects models will be conducted. For each model, we will include main effects of timepoint and medication group, as well as an interaction term. If the two treatment groups are systematically different on demographic or use characteristics at baseline, these measures will be included as covariates in the analysis. Models will involve a random intercept. Mixed effects models will also be used to compare drug cue reactivity at baseline and during the final week.

Secondary Aim 2. To compare SUVO 20mg to placebo on number of adverse events experienced, t-tests will be used.

Power analysis and sample size. A sample size of 40 will be used in this study. For all aims, we are sufficiently powered to detect moderate-to-strong effect, which has been observed in

Date: 09/19/2024

Principal Investigator: [name].

Application Number: IRB00341328

previous studies (e.g., Huhn et al., 2022). Due to our smaller sample size, effect size measures will also be considered.

All analyses will be conducted in SPSS and R. Two-tailed tests and an alpha level of .05 will be used.

d. Early stopping rules.

Participants will discontinue the study if the medical team determines it is not safe to continue in the study or if they request to discharge from the study. Additional stopping rules will include not abiding by study policies and procedures, or engaging in behaviors towards staff or other participants that are abusive. Finally, development of an intercurrent illness or condition that changes the participant's risk profile may result in a medically-related discharge from the study.

8. Risks

a. Medical risks, listing all procedures, their major and minor risks and expected frequency.

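### Section 7c specifies only a random intercept and leaves the time coding open, so the timepoint-by-group test can exceed the stated .05 for outcomes with more than two timepoints

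*Combined protocol and SAP*

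**What the plan says.** Section 7c plans mixed models for craving, urine results, insomnia, sleep continuity and affect. The fixed part is "main effects of timepoint and medication group, as well as an interaction term". On the random part there is one sentence, "Models will involve a random intercept", given under Primary Aim 1 and repeated under Secondary Aims 1 and 3. No random slope, residual covariance, robust standard error or degrees-of-freedom method is named. All tests share one rule: "Two-tailed tests and an alpha level of .05 will be used". On size, "A sample size of 40 will be used in this study"; the allocation ratio is not stated.

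Three things are left open:
- whether timepoint is a linear trend or a set of visit categories;
- whether the interaction, the group effect or another contrast decides;
- whether sleep enters as nightly values or as summaries.

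Section 4c gives 8 twice-weekly visits on treatment. Section 4a has nightly sleep diaries. Cue reactivity is compared at two occasions only, baseline and final week.

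**The concern.** A random intercept on its own assumes that any two visits of one person are equally correlated and that everyone in an arm shares one time trend. Repeated craving scores, drug screens and sleep measures may well break both assumptions: values close in time tend to resemble each other, and people drift at different rates. The model then treats a person's visits as more independent evidence about change than they are, and the standard error of the timepoint-by-group term comes out too small.

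That term shows whether the arms diverge over treatment. If its error rate is not controlled, the nominal .05 is not delivered even for a single outcome, and a pilot meant to inform scale-up may point the wrong way. Because the time coding is also open, an analyst could choose, after seeing data, between tests with quite different error rates.

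**Working it through.** **Inputs.** From the documents: N = 40, 8 on-treatment visits, 28-30 nights, two-sided .05. Assumed, because the documents give no figures: 20 per arm, complete and equally spaced data, residual SD σ = 15, SD of personal change from first to last visit τ = 0 or 20 (τ/σ = 1.33), lag-1 residual correlation ρ = 0 to 0.7. The between-person SD drops out of a within-person test.

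**The plan's own figure.** The only one is alpha = .05, which is assigned, not derived. The check is whether the specified model delivers it.

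**Formula, linear time.** Code time from 0 to 1 over T visits, centre it as x, and let S = Σx². For T = 8, S = 42/49 = 0.857. With V the within-person covariance and C the centring matrix:
- true variance of one person's slope: v = x′Vx / S²;
- residual mean square of the random-intercept fit: M = [N·tr(CV) − 2·x′Vx/S] / [N(T−1) − 2];
- slope variance that the fit assumes: M/S;
- ratio R = v/(M/S), and rejection rate ≈ 2[1 − Φ(1.96/√R)].

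**Worked case: varying trends only, τ = σ = 1.** v = 1 + 1/0.857 = 2.167. M = 1 + 0.857 × 38/278 = 1.117. M/S = 1.303. R = 2.167/1.303 = 1.66 and √R = 1.289. The rejection rate is 2[1 − Φ(1.520)] = 12.9%. Simulation gave 12.4%.

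**8 visits, linear time.**

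| ρ | τ/σ | R | Formula | Simulated |
|---|---|---|---|---|
| 0 | 0 | 1.00 | 5.0% | 5.3% |
| 0.3 | 0 | 1.58 | 11.9% | 11.4% |
| 0.5 | 0 | 2.16 | 18.2% | 18.5% |
| 0.7 | 0 | 2.92 | 25.2% | 26.0% |
| 0.3 | 1.33 | 2.66 | 23.0% | 23% |
| 0.5 | 1.33 | 3.24 | 27.6% | 28% |
| 0.7 | 1.33 | 4.07 | 33.2% | 33% |

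So the model keeps 5% when its assumptions hold, and reaches about 33% at the far corner.

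**8 visits, categorical time** (7-df F test): 4.7% with no extra correlation; 6.0%, 7.1% and 9.3% at ρ = 0.3, 0.5 and 0.7. Adding varying trends takes the extreme corner to about 11%.

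**Binary screens** (random-intercept logistic, likelihood-ratio test, linear time, 500 runs): 5.0% with no extra correlation; 7.2%, 12.8% and 16.6% at latent ρ = 0.3, 0.5 and 0.7; 7.2%, 10.0% and 13.6% for a logit-slope SD of 1, 2 and 3 over the study. Monte Carlo error is about 1-1.7 points.

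**Nightly rows, if modelled** (T = 28): with linear time about 5% with no extra correlation, 24% at ρ = 0.5, 38% at ρ = 0.7, and about 50% at ρ = 0.7 with τ/σ = 1.33. With categorical time about 5-17%, the top value needing ρ = 0.8.

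**Two timepoints (cue reactivity).** Each person has a single difference, so R = 1 whatever ρ and τ are. Simulation gave 4.6-5.5%.

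**Does the remedy work?** A two-sample t-test on per-person slopes, the balanced-data equivalent of adding a random slope, stayed at 4.3-5.9% in every scenario from 2 to 30 timepoints. Comparing per-person means stayed at 4-6%.

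**The case against.** The strongest reply is that the size rests on quantities the documents do not contain. That stands. Under equal correlation and common trends the rate is 5%, and mild departures at 8 visits give 7.7-9.1%. A reader might infer that the test simply has a false-positive rate of 13-33%. The documents do not support that: it needs linear time, which 7c never states, and at least moderate assumed correlation or trend variation.

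Four further points also stand:
- A reader might take every repeated-measures model to be affected. The two-occasion cue-reactivity models, a primary outcome, are not.
- A reader might quote 40-50% for sleep. No section says that nightly rows are modelled. Section 7b describes reports on the night before the assessment, and Section 4a says the nightly diaries serve actigraphy scoring.
- The interaction is not named as the deciding test. With balanced data and categorical time, the group effect averaged over visits is a comparison of per-person means, which keeps about 5%.
- Section 7a says "The average score across each visual analogue scale will be a primary outcome". This may mean averaging within a scale at a visit. It does not clearly name an average over visits, so it cannot be used to say that 7c departs from 7a.

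It can also be said that silence is not exclusion, and that this is a pilot that will consider effect sizes too. Yet 7c addresses within-person correlation twice and names one structure each time. The same understated standard error also narrows the intervals around those effect sizes.

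**Conclusion.** The concern holds in conditional form. With a random intercept as the only named structure, the timepoint-by-group test for outcomes with more than two timepoints is not protected at .05. Under the assumptions above, the rate over 8 visits is about 5-33% with linear time and about 5-10% with categorical time (11% at the extreme corner). For binary screens with linear time it is about 7-17% when extra correlation is present. If nightly sleep rows were modelled, which the plan does not say, it would be about 5-50% with linear time and 5-17% with categorical time. Cue reactivity is unaffected.

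These are ranges over assumed values, not estimates for this trial. The direction is firm, because each such departure makes the test too liberal; the size is not known. This should be fixed before unblinding, but it does not by itself invalidate the design.

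**What to change.** In Section 7c:

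1. State how timepoint is coded and which contrast decides, for each outcome.
2. For any linear timepoint-by-group test, add a participant-level random slope for time with Kenward-Roger degrees of freedom. If the fit fails, fall back on a between-arm comparison of per-participant slopes. If visits are categorical, use an unstructured covariance for the 8 visits (8 × 9/2 = 36 parameters), with a simpler fallback stated in advance.
3. Reduce nightly sleep to weekly or whole-period participant means before modelling. An unstructured matrix for 28 nights would need 28 × 29/2 = 406 parameters from 40 people.
4. For the binary models, add a random slope or use small-sample-corrected robust standard errors.

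Do not rely on an AR(1) residual alone, since it does not model differing personal trends. In one small simulation with a personal-change SD of 20, not repeated, it still rejected 7-10% at 8 visits and about 17% at 28 nights.

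A between-arm comparison of per-participant post-baseline means may be added as a supporting test. It answers a different question from the interaction, so it should not silently replace it.

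Cost: SAP wording and a few lines of code, somewhat wider intervals, and occasional use of a fallback.

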2. Objectives (include all primary and secondary objectives)

Primary Aim 1. Examine whether individuals who are randomly assigned to SUVO 20mg (oral) will be less likely to test positive for (i) cocaine and (ii) non-prescribed opioids on urine drug screens (UDS) and will self-report lower opioid and cocaine craving, relative to those receiving placebo.

Date: 09/19/2024

Principal Investigator: [name].

Application Number: IRB00341328

Secondary Aim 1. Examine whether, relative to placebo, SUVO 20mg will improve self-reported sleep quality and total sleep time, as assessed via a sleep diary and an actigraph-like device, and will reduce self-reported insomnia symptoms and wake after sleep onset (WASO).

Secondary Aim 2. Given previous work suggesting that Suvorexant has a good safety profile among patients using opioids and patients using cocaine, a secondary aim will test no between-group differences in the rate of adverse events between individuals assigned to Suvorexant and placebo.

Secondary Aim 3. Examine whether SUVO 20mg will be associated with lower stress reactivity, lower self-reported stress and negative affect, and greater positive affect, relative to placebo.

3. Background (briefly describe pre-clinical and clinical data, current experience with procedures, drug or device, and any other relevant information to justify the research)

Opioid/stimulant co-use is a public health crisis that is increasing in prevalence (Goodwin et al., 2021) and directly contributing to increases in overdose deaths and disproportionately impacting minority individuals (Townsend et al., 2022). Individuals engaged in opioid/stimulant co-use face a greater risk of treatment discontinuation and continued substance use (Levin et al., 2015).

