Suvorexant is a Schedule IV dual orexin receptor antagonist (DORA) that is FDA-approved for the treatment of insomnia. Suvorexant is 82% bioavailable and has a Tmax of 2 hours. Tmax can be delayed by food though this does not impact the Cmax. It is extensively metabolized by the liver through CYP3A enzymes. The elimination half-life is 12 hours, and it is excreted through both renal (23% unchanged) and fecal (66%) means. Suvorexant is contraindicated with other CNS depressants and alcohol and strong CYP3A inhibitors. It is rated pregnancy category C, indicating insufficient data available to make determination for human subjects. Suvorexant is contraindicated in patients with narcolepsy, patients with recent suicidal behavior, or patients with severe hepatic impairment. There is no evidence of potential overdose and a toxic dose has not been established. Clinical trials that administered up to 240mg of suvorexant reported no overdose effects, though there was a dose-dependent increase in the frequency and duration of next day somnolence. As per product label, most common side effects are sleepiness/drowsiness (7% of people), headache (7%), dizziness (3%), diarrhea (2%), dry mouth (2%), upper respiratory infection (2%), abnormal dreams (2%), and cough (2%). Serious adverse effects include sleep paralysis (7%), somnolence (7%), and worsening of depression or suicidal ideation.

b. Steps taken to minimize the risks.

Individuals with medical or psychiatric contraindications and/or individuals who are taking exclusionary medications (including CNS depressants such as benzodiazepines or other sleep medications), individuals with co-occurring moderate or severe substance use disorder, those with current and major psychiatric illness (e.g., bipolar disorder) or past 30-day suicidal behaviors are excluded for participating. Participants will be provided the maximum FDA-approved dose (20mg). All medication will be dispensed in two (10mg) capsules and participants will be informed they can refuse reduce from 2 to 1 capsule or stop taking medication at any point and we will track participant acceptance (e.g., in terms of adherence with dosing schedule) of the medication as part of the study. Given that suvorexant can cause next-day drowsiness, participants will be explicitly instructed not to drive or operate heavy machinery under any circumstances within 8 hours of taking suvorexant for the first time, or if they continue to feel

Date: 09/19/2024

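### Secondary Aim 2 is worded to show no difference in adverse events, but its only analysis is a difference test with no interval or reading rule

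*Combined protocol and SAP*

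**What the plan says.** Section 2 (Objectives, Secondary Aim 2) starts from an expectation, "Given previous work suggesting that Suvorexant has a good safety profile among patients using opioids and patients using cocaine", and then sets the aim: "a secondary aim will test no between-group differences in the rate of adverse events between individuals assigned to Suvorexant and placebo". The Abstract points the same way, since it expects no side effects from suvorexant.

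The whole analysis for this aim is one sentence in section 7c: "To compare SUVO 20mg to placebo on number of adverse events experienced, t-tests will be used". The general rule at the end of 7c applies to it: "Two-tailed tests and an alpha level of .05 will be used".

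Two other sentences in 7c bear on the point. One is a power statement: "For all aims, we are sufficiently powered to detect moderate-to-strong effect". The other is a general remark: "Due to our smaller sample size, effect size measures will also be considered". Neither names an interval, a margin or a way to read a non-significant result, and neither is specific to adverse events. Sections 7b and 8b describe how events are collected, documented and reviewed. The safety threshold in 8b triggers a medical consultation about an individual event and is not a margin for comparing arms.

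**The concern.** The aim's hypothesis and the test's null hypothesis are the same statement. A two-tailed t-test starts from no difference and asks whether the data contradict it. If they do not, the null has survived but has not been shown. The result the trial expects is therefore one that its only planned analysis cannot support.

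The documents nowhere say outright that a non-significant p-value will be reported as equal safety. But the aim is worded as if it would be, and nothing in 7c prevents it. The power statement may add to the risk, because a reader could take a null result from a study described as adequately powered for all aims as reassurance. That statement concerns detecting an effect, not ruling one out.

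At stake is the safety conclusion carried forward from this pilot, which the Abstract presents as informing wider use. The choice of a t-test for event counts is not the objection.

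**Working it through.** **Logic.** Aim (section 2): no difference in the adverse-event rate. Analysis (7c): a test whose null is no difference. This mismatch follows from the wording and needs no figures. The arithmetic below only shows what a null result would leave open with 40 participants.

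**The plan's own figure.** N = 40 cannot be reproduced, because 7c gives no numerical effect size or power. With an assumed 20 per arm and two-sided .05, exact t-test power is 34% for a standardised difference of 0.5 and 69% for 0.8. The difference detectable with 80% power is 0.91 SD.

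**Inputs.**
- From the documents: N = 40; two-tailed alpha .05; t-test on counts (all 7c).
- Section 8a lists label percentages for single side effects of suvorexant: 7 + 7 + 3 + 2 + 2 + 2 + 2 + 2 = 27%. This is neither an all-cause rate nor a placebo rate. It only suggests a low end for the range.
- Not given, so assumed: 1:1 allocation (section 4a says only "participants will be randomized (stratified by gender) to receive 20mg of SUVO (the maximum FDA approved dose) or placebo"), full follow-up, placebo means of 0.25 to 3 events per person, and either Poisson counts (variance = mean) or overdispersed counts (negative binomial, variance = mean + mean squared).
- The 50% excess is an illustrative benchmark, not a figure from the plan.

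**Hand check at placebo mean 1.** The critical t value on 38 degrees of freedom is 2.024.

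*Chance of missing a true 50% excess (means 1.0 and 1.5):*
- Poisson: SE = √((1 + 1.5)/20) = 0.354; 0.5/0.354 = 1.414; power ≈ Φ(1.414 − 2.024) = Φ(−0.610) = 0.27, so about 73% non-significant.
- Overdispersed: variances 2 and 3.75; SE = √(5.75/20) = 0.536; 0.5/0.536 = 0.933; power ≈ Φ(0.933 − 2.024) = Φ(−1.091) = 0.14, so about 86% non-significant.

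*95% interval when the arms are truly equal:*
- Poisson: half-width ≈ 2.024 × √(2/20) = 0.64 events per person.
- Overdispersed: half-width ≈ 2.024 × √(4/20) = 0.91.
- To exclude +0.5 events, the observed difference must be below 0.5 − 0.64 = −0.14 (Poisson). The chance is Φ(−0.14/0.316) = Φ(−0.443) = 0.33.

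**Simulation** (40,000 trials per setting, pooled two-sided t-test, 20 per arm):

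| Placebo mean | 50% excess non-significant: Poisson | Overdispersed | Equal arms, mean half-width: Poisson | Overdispersed | Equal arms, 50% excess excluded: Poisson | Overdispersed |
|---|---|---|---|---|---|---|
| 0.25 | 90% | 92% | 0.31 | 0.35 | 12.5% | 12% |
| 0.5 | 84% | 89% | 0.45 | 0.54 | 20% | 16% |
| 1 | 72% | 87% | 0.63 | 0.88 | 34% | 22% |
| 2 | 51% | 84% | 0.90 | 1.53 | 59% | 27% |
| 3 | 33% | 83% | 1.10 | 2.17 | 77% | 30% |

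The simulation agrees with the hand check at mean 1.

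**Sensitivity to allocation.** At mean 1, suvorexant:placebo splits of 16:24, 24:16 and 27:13 give 72%, 74% and 78% non-significant (Poisson) and 85%, 89% and 92% (overdispersed).

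**Is the t-test sound here?** With equal arms the type I error was 4.5% to 5.1%. Coverage of its 95% interval was 93.9% to 95.5% at 20 per arm and 93.4% to 96.7% under the unequal splits. The interval can therefore be taken from the planned test.

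**The case against.** The strongest reply is that the aim is only loosely phrased. Testing no between-group differences can mean testing the null of no difference, which a two-tailed t-test does. The sentence in 7c is neutral, and expecting a result is not a rule for interpreting one. 7c also says that effect sizes will be considered, so the authors do not plan to rely on p-values alone. The stakes are small: section 6c says the study is not intended for FDA reporting as a well-controlled study, and participants are protected by the daily memos, weekly review and immediate medical consultation in 8b. Finally, the event rates, the dispersion and the 50% benchmark are all assumed, and the results vary widely with them.

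Much of this stands. The stakes are limited, no passage commits to a misreading, and the figures are illustrations. At a Poisson mean of 3 with equal arms, the interval would exclude a 50% excess in 77% of trials, so the gap is not equally serious in every setting. A margin is not needed once the aim is worded as estimation.

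Two things do not go away. Even on the ordinary null-test reading, the expected result remains one the analysis cannot support. And an effect size without an interval does not show which differences the data still allow.

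**Conclusion.** The concern holds, with high confidence, because it rests on the wording of section 2 and section 7c and not on any assumed number. The aim expects no difference, the only analysis is a difference test, and the plan supplies no interval, margin or reading rule.

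The practical size depends on event rates the documents do not give. Under the assumptions used (20 per arm, full follow-up, placebo means 0.25 to 3), a true 50% excess would be missed in 33% to 90% of trials if counts are Poisson and 83% to 92% if overdispersed. A non-significant result would usually remain compatible with such an excess unless events are frequent and not overdispersed.

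The weight is low to moderate: a secondary aim in a pilot, with participant safety handled separately. The change should still be made, because it alters what the trial can conclude about safety at almost no cost.

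**What to change.** 1. In section 2, reword Secondary Aim 2 as estimating the between-group difference in adverse events.
2. In section 7c, state that the mean difference in adverse events per participant will be reported with its 95% confidence interval from the planned t-test.
3. In section 7c, add that a non-significant result will not be read as evidence of no difference or of equal safety.

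Optional and minor: the aim speaks of a rate while the analysis uses a count, and time on study can vary through the exit-visit window (4a) and early removal (4g). A rate ratio with a 95% confidence interval, using days on study as an offset, could be reported as well. Raw counts are biased only if time on study differs between arms, and the bias could go either way.

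Cost: one reworded sentence and two added ones. No new data, visits, test or software are needed; the optional rate ratio needs days on study derived per participant. The drawback is that the interval will be wide, so a claim of no difference probably cannot be made with 40 participants unless events are frequent and not overdispersed.
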